8.1.3 Unexpected Adverse Event

An unexpected AE is any AE that the investigator defines as related to a study medication, the nature of which is not consistent with the Investigator's Brochure or package insert.

8.1.4 Adverse Events of Special Interest

The following are considered AEs of special interest, based on the route of administration, toxicology profile for NFX-179: adverse events related to kidneys, liver, coagulation, and the immune system. Reference is made to the IB for further details.

8.2 Reporting Adverse Events

The investigator is responsible for ensuring that all AEs and SAEs are recorded in the subject's medical record, AE CRF, and SAE form (if applicable), and reported to NFFlection. The AE CRF must be used to report both AEs and SAEs. SAEs must also be reported on the appropriate SAE form.

8.2.1 Adverse event reporting period

The investigator must start reporting non-serious AEs and SAEs from the time of the start of the subject's first study medication application until the end of the subject's study participation, or until 30 days after the last study medication application, whichever is longer, whether or not they are considered related to the study.

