
Criteria for Evaluation
	
Safety Assessments:
 
Adverse Events: During the study, subjects will be assessed for the occurrence of new and ongoing AEs. Descriptions of AEs will include the date(s) of onset and resolution (if resolved), maximum severity, and seriousness, action taken regarding the study drug, corrective treatment, outcome, and the investigator’s assessment of causality. AEs present at any visit will be followed to resolution

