5.4 Subject discontinuation from the study

Subjects will be informed that they are free to withdraw from the study at any time and for any reason.

The investigator may remove a subject from the study if, in the investigator's opinion, it is not in the best interest of the subject to continue the study. The investigator must remove a subject from the study if the subject experiences:

- A Serious Adverse Event the investigator defines as related to the study medication, regardless of the intensity of the event
- A non-serious adverse event the investigator defines as related to study medication that has a severity of severe and requires treatment to resolve.

Examples of other reasons subjects may be discontinued from the study are a change in compliance with an inclusion or exclusion criterion, occurrence of AEs, occurrence of pregnancy or use of a prohibited therapy. Notification of discontinuation will immediately (within 24 hours) be made to the study monitor.

All withdrawn subjects with ongoing AEs will be followed as appropriate.

The study may be discontinued at the discretion of NFllection. Some examples of reasons for discontinuation are the occurrence of the following:

- Increased frequency, severity, or duration of known AEs
- Medical, regulatory, or ethical reasons affecting the continued performance of the study
- Difficulties in the recruitment of subjects.

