5.4.3 Early Termination Visit

The investigator should complete the following study procedures for randomized subjects who prematurely discontinue from the study:

- For subjects who discontinue from the study prior to Visit 8, complete the Visit 8 procedures
- For subjects who complete Visit 8 and discontinue from the study prior to Visit 9 complete the Visit 9 procedures.

Detailed instructions for documenting subjects who prematurely discontinue from the study will be included in the CRF completion guidelines.

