An investigational center staff member will weigh each study medication tube when dispensed, at each study visit, and when returned using the provided scale (or equivalent). The study medication container weight must be reported to the nearest 0.1 g. The study medication tubes must be weighed with the label attached and the cap on and without any other packaging.

At Visit 2, the study medication tube dispensed to the subject must be weighed pre subject application of study medication and post subject application of study medication.

The scale used to weigh the study medication tubes must be calibrated, according to the instructions provided for the scale, and the calibration documented, each day the scale is used, prior to use. Any scale that does not pass the calibration test must not be used to weigh the study medication.

5.6.7 *Route of Administration, frequency and treatment period*

The study medications are applied topically to each Target cNF, once daily for 182 days (26 weeks).

5.6.8 *Study medication application*

The study medications are for external, topical use on each Target cNF only and on the appropriate study subject only.

To perform a study medication application the subject should:

- Wash her/his hands before starting the application
- Avoid applying the study medication to any open wounds or obviously infected skin
- Apply an amount of the assigned study medication sufficient to cover each Target cNF with a thin layer of the study medication
- Gently rub in the study medication until no visible accumulation is evident
- Wash her/his hands after completing the application.

The subject must apply study medication to the entire area of each Target cNF limiting exposure to the un-affected skin surrounding the cNF.

At Visit 2, an investigational center staff member will instruct the subject on the proper application technique and observe the subject's study medication application to ensure proper

application technique and record the time the subject completes the application to the last Target cNF as the Application Completion Time. A staff member will monitor the subject for adverse events for at least 20 minutes after the Application Completion Time.

Subjects should continue QD application of the assigned study medication to each Target cNF for 182 days (26 weeks) with 18-30 hours between applications.

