13. Measure the dimensions of each Target cNF
14. Take standardized photographs of each Target cNF
15. Weigh study medication
16. Collect all study medication
17. Review the study instructions with the subject. If the subject wishes to be contacted about participation in the exit interview study inform the identified individual at the exit interview vendor that the subject has completed study participation and provide them with the subject's contact information
18. Schedule the next study visit.

6.2.9 Visit 9/Day 211/Week 30 (End of study, early termination if subject completes Visit 8 and discontinues from the study prior to Visit 9)

This visit must occur 210 days (± 4 days) after Visit 2.

At this visit, the investigator or designee will perform the following procedures:

1. Query the subject in a non-directive manner about any changes in her/his health since the previous visit and report all AEs as appropriate
2. Query the subject about any changes in her/his concomitant therapies since the previous visit and report changes as appropriate
3. Confirm the subject has followed all study instructions
4. Measure vital signs
5. Perform a urine pregnancy test for WOCBP
6. Confirm the location of each Target cNF
7. Have the subject perform an LTA of the symptoms for each Target cNF
8. The investigator will perform an LTA of the signs for each Target cNF
9. Measure the dimensions of each Target cNF
10. Take standardized photographs of each Target cNF
11. Perform a PTA for each Target cNF
12. Have the subject perform a SSA for each Target cNF
13. Discharge the subject from the study.

6.2.10 *Unscheduled Visit*

The investigator may see a subject for an unscheduled study visit at any time it is necessary, in the investigator's opinion.

At unscheduled visits, the investigator or designee will perform the following procedures, at a minimum:

1. Query the subject in a non-directive manner about any changes in her/his health since the previous visit and report all AEs as appropriate
2. Query the subject about any changes in her/his concomitant therapies since the previous visit and report changes as appropriate
3. Review the study instructions with the subject
4. Schedule the next study visit.

Complete other study procedures that are, in the investigator's opinion, appropriate for the visit. Detailed instructions for documenting unscheduled visits will be included in the CRF completion guidelines.

6.3 **Target cNF identification**

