8.6 Pregnancy

Medical Monitor

SAE Email: [REDACTED]

24-hour telephone: [REDACTED]

If a female subject becomes pregnant during the treatment period or within 6 months after the last study medication application, a Pregnancy Report form should be completed. While not an AE or SAE the investigator must submit the completed Pregnancy Report form to the Medical Monitor within 24 hours of learning of the pregnancy.

Abortion, whether therapeutic or spontaneous, will also be reported on a Pregnancy Report form and sent to the Medical Monitor. If the abortion meets seriousness criteria, this information will be captured on the AE CRF and SAE form.

Any congenital anomaly/birth defect in a child born to a female subject should be recorded and reported as an SAE.

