
If, following the first study medication application it is determined that the subject may have been or was pregnant at the time of study medication exposure (including 30 days after the last study medication application) the investigator must immediately notify the Medical Monitor and record the pregnancy on a pregnancy surveillance form. While not an AE or SAE, the investigator must report every pregnancy using a pregnancy surveillance form and follow the same reporting procedures as described for reporting an SAE.

Protocol-required procedures for trial discontinuation and follow-up must be performed on the subject unless contraindicated by pregnancy (*e.g.*, x-ray studies). Other appropriate pregnancy follow-up procedures should be considered if indicated. In addition, the investigator must report follow-up information regarding the course of the pregnancy, including perinatal and neonatal outcome on the pregnancy surveillance form. Infants should be followed for a minimum of six weeks.

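### Scheduled contact does not secure the protocol's own 30-day adverse event window, and the pregnancy-reporting and AE follow-up rules differ between sections

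*Combined protocol and SAP*

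**What the plan says.** **Reporting window.** Section 8.2.1 starts AE and SAE reporting at the first application. It ends reporting at the end of participation or "until 30 days after the last study medication application, whichever is longer", whether or not the event is considered related. Section 8.4 has the investigator elicit AEs by a non-directive question at each post-randomization visit.

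**Completers.** Section 5.6.8 sets 182 days of once-daily application. Visit 8 is 182 ± 4 days after Visit 2 (6.2.8), and all study medication is collected there. For Visit 9, section 6.2.9 says "This visit must occur 210 days" (± 4) after Visit 2, and its last step is discharge.

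**Early leavers.** Section 5.4.3 says: "For subjects who discontinue from the study prior to Visit 8, complete the Visit 8 procedures". It lists nothing after that visit for this group. Under 5.4, "The investigator must remove a subject from the study if the subject experiences" a related SAE, or a severe related non-serious AE that needs treatment. Section 5.7.2 also discharges any subject whose blind is broken.

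**Pregnancy.** Section 8.6 calls for a Pregnancy Report form "If a female subject becomes pregnant during the treatment period or within 6 months after the last study medication application". Section 8.6.2 addresses pregnancy at the time of exposure, "including 30 days after the last study medication application", and names a pregnancy surveillance form.

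**Follow-up of known AEs.** The synopsis (Criteria for Evaluation) says "AEs present at any visit will be followed to resolution" or until clinically stable, with no distinction by causality. Section 8.4 follows unrelated AEs only until they resolve or the subject has the last study visit.

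**The concern.** The protocol states a minimum 30-day post-treatment window, but its means of finding events is the visit question, and the visits are not tied to the last application. An event that begins after the last visit but inside the window reaches the database only if the subject volunteers it or an unscheduled visit happens to occur.

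The gap matters most for subjects who stop before Visit 8, because they include those removed for drug-related reasons. Safety against vehicle is a primary objective (section 3). Section 9.3.6 defines treatment-emergent AEs with a start but no end date and summarizes them by number of subjects, with no stated allowance for unequal observation time. If departures before Visit 8 were more frequent on active gel, post-treatment events would be missed more often there.

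The two pregnancy triggers and the two follow-up rules raise a separate problem: sites reading different sections could collect different data.

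**Working it through.** **The plan's own figure.** Maximum participation in 4.4 is 242 days. Screening 28 + treatment 182 + follow-up 28 + window 4 = 242. By way of Visit 9, 28 + 210 + 4 = 242. The figure reproduces, so Visit 9 is the last contact that the stated duration provides for.

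**Calendar.** Visit 2 is Day 1, so *k* days after Visit 2 is Day *k* + 1. Visit 8 may fall on Days 179 to 187 (nominal 183) and Visit 9 on Days 207 to 215 (nominal 211).

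Gap = Visit 9 day − day of last application.

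**Nominal dates.**
- Last application on Day 182: 211 − 182 = 29 days, 1 day short of 30.
- Last application on the Visit 8 day: 211 − 183 = 28 days, 2 days short.

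**Visit 9 window, last application on Day 182.**

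| Visit 9 day | 207 | 208 | 209 | 210 | 211 | 212 | 213 | 214 | 215 |
|---|---|---|---|---|---|---|---|---|---|
| Days since last application | 25 | 26 | 27 | 28 | 29 | 30 | 31 | 32 | 33 |

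Five of the 9 permitted days fall before day 30. The largest shortfall is 30 − 25 = 5 days.

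**Sensitivity to the last application day.** The documents do not fix that day exactly when Visit 8 is early or late. The table takes all 9 × 9 = 81 permitted pairs of Visit 8 and Visit 9 days. These are counts of dates, not probabilities.

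| Assumed last application | Gap, days | Pairs under 30 days |
|---|---|---|
| Earlier of Day 182 and the day before Visit 8 | 25 to 37 | 35 of 81 |
| Day before Visit 8 | 21 to 37 | 45 of 81 |
| Visit 8 day itself | 20 to 36 | 53 of 81 |

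For the first row, the pairs reaching 30 days number 8 + 7 + 6 + 5 for Visit 8 on Days 179 to 182, plus 5 × 4 for Days 183 to 187. That is 46, and 81 − 46 = 35. Under every assumption a substantial share of compliant schedules ends before day 30, and a substantial share does not.

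**Early leavers.** Section 5.1 plans about 168 randomized and at least 150 completing: 168 − 150 = 18, and 18/168 = 10.7%. This allowance covers all non-completion, so it is a ceiling for those who leave before Visit 8. Scheduled visits after their termination visit: none.

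**Pregnancy.** Six months is about 365.25/2 = 182.6 days, against 30 in 8.6.2. The last scheduled test is at Visit 9, about 28 days after the last application, so about 182.6 − 28 = 154.6 days (roughly 5 months) of the longer window has no scheduled contact. The instruction in 8.6.2 to call the site about a suspected pregnancy applies during the trial.

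**The case against.** Section 8.2.1 is a reporting duty, not a visit schedule, and it expressly allows the duty to outlast participation. Section 8.5 applies whenever the investigator becomes aware of an SAE, and 6.2.10 permits unscheduled visits at any time. So the text is not contradictory on its face. That is fair, but a duty to report does not find events, and the only elicitation described is at visits.

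A reader might infer more than the documents support in five places:

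- *Early leavers have no off-treatment contact at all.* Not so. Section 5.4 follows withdrawn subjects with ongoing AEs, 8.4 follows unresolved related AEs to resolution or stability, and 8.5 follows SAEs until the Medical Monitor agrees. Under 5.6.9 applications may stop before a subject is removed, so the termination visit may itself come after the last application. What is missing is elicitation of new events after that visit.
- *Completers may be discharged 20 days after treatment.* Twenty days is the shortest Visit 8 to Visit 9 interval. It applies only if applications continue to a late Visit 8, beyond the 182-day course. With the last application on Day 182 the minimum is 25 days.
- *The plan's 28-day off-treatment safety comparison is biased toward no difference.* Section 9 specifies no such comparison; safety is summarized descriptively. The direction of any bias depends on departures differing by arm, which is unknown. Section 2.2.2 reports no treatment-related TEAEs in the earlier 28-day study.
- *Eighteen subjects are affected.* Eighteen is the planning allowance for every kind of non-completion, including loss to follow-up and departures after Visit 8. The latter have Visit 9 procedures (5.4.3).
- *The 30-day contraception period contradicts the 6-month pregnancy window.* Contraception is a separate rule and is not itself in conflict.

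On pregnancy, it can be argued that 8.6.2 cases fall inside the 8.6 window and that 8.6.2 also asks for every pregnancy to be reported, so a site could satisfy both. That limits the harm. The windows and form names still differ.

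**Conclusion.** The concern holds in a limited form. The schedule does not secure the 30-day window that 8.2.1 requires. For completers the shortfall is small: 1 to 2 days on nominal dates and at most 5 days if the last application is on Day 182. It is also not universal, since Visit 9 on Days 212 to 215 then reaches day 30. For subjects who leave before Visit 8 the gap is more substantial, because no contact is scheduled after the termination visit. They number at most about 18 of 168 and include those removed for related SAEs or severe related AEs. Whether this distorts the active-versus-vehicle safety summary cannot be told from the documents.

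The mismatches between 8.6 and 8.6.2, and between the synopsis and 8.4, are plain on the text and need reconciling.

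The conclusion assumes that the visit-by-visit procedures in 6.2 are complete. The schedule of events table (6.1) and the CRF completion guidelines were not available for this check; a later contact specified there would answer the first part.

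**What to change.** - Reconcile 5.4.3 and 6.2.9 with 8.2.1, so that AE elicitation covers the stated window for both completers and early leavers. One way is a single documented contact by existing site staff at the end of that window, needed only when the subject's last visit falls earlier.
- Reconcile 8.6 with 8.6.2 on the pregnancy-reporting window and the form to be used. The choice of window is the sponsor's.
- Reconcile the synopsis with 8.4 on how long unrelated AEs are followed. That choice is also the sponsor's.

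The cost is protocol wording and a short call for some subjects. Some early leavers may not be reachable, and a few more AEs will be recorded. Dose, treatment duration and removal rules need not change.

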8.3 Assessment of Adverse Events

The investigator is responsible for assessing the severity, seriousness, and causality of AEs.

8.3.1 Severity of Adverse Events

The investigator is to define the severity of each AE using the following definitions as a guideline. The investigator will consider the range of the possible severity of the event and identify the severity that is the most appropriate according to her/his medical judgment:

- **Mild** – Awareness of signs or symptom, but easily tolerated
- **Moderate** – Discomfort, enough to cause interference with usual activity
- **Severe** – Incapacitating with inability to perform usual activity.

8.3.2 *Relationship to Study Medication*

The investigator will determine if there is a reasonable causal relationship between the study medication and an AE or not. The investigator will use her/his best medical judgment and consider all relevant factors (*e.g.*, temporal relationship, location of the event, the subject's relevant medical history, concomitant therapies, and concurrent conditions) to determine the relationship of the AE to the study medication.

The investigator will define the relationship of an AE to the study medication by selecting one of the following categories:

- **Related** – There is a reasonable causal relationship between the study medication and the AE
- **Not Related** – There is not a reasonable causal relationship between the study medication and the AE.

The expression “reasonable causal relationship” is meant to convey in general that there are facts (evidence) or arguments to suggest a causal relationship.

8.4 **Procedures for reporting non-serious adverse events**

At each post-randomization visit, the investigator will question the subject to elicit AEs using a non-directive question such as “Has there been any change in your health since the previous study visit?” If appropriate, based on the subject's response to non-directed questioning to elicit AEs, the investigator will follow-up with directed questions and appropriate evaluations.

Any AE noted during the reporting period must be reported in the source documents and on the appropriate AE CRF. AEs that are defined as “Not Related” to the study medication will be followed until they are resolved or until the subject's last study visit. AEs that are defined as “Related” to the study medication will be followed until they are resolved or, if not resolved after the subject's last study visit, until in the opinion of the investigator, the AE reaches a clinically stable outcome with or without sequelae.

8.5 Procedures for reporting serious adverse events

Medical Monitor

SAE Email: [REDACTED]

24-hour telephone: [REDACTED]

Upon becoming aware of a SAE occurring during the AE reporting period, whether or not related to the study medications, the investigator must:

1. Take the appropriate medical action to ensure the subject's safety.
2. Immediately inform the Medical Monitor of the SAE by email (SAE Email address above), ensuring that the subject information is deidentified (only subject initials and subject identifier)
3. Print a copy of the email and place in the study file.
4. Within 24 hours complete, as fully as possible, an AE CRF and an SAE form; e-mail the forms and any other relevant documentation (*e.g.*, concomitant medication CRF, medical history CRF, laboratory test results, etc.) to the Medical Monitor.
5. Monitor and document the progress of the SAE until it resolves or, if not resolved after the subject's last study visit, until in the opinion of the investigator the SAE reaches a clinically stable outcome with or without sequelae AND the investigator and Medical Monitor agree that the SAE is satisfactorily resolved.
6. Inform the Medical Monitor of SAE updates, via telephone, followed by an SAE form update sent by e-mail.
7. Comply with the appropriate regulatory requirements and NFlexion instructions regarding reporting of the SAE to the responsible Institutional Review Board (IRB) or Ethics Committee (EC).

The investigator will define the severity of every AE as Mild, Moderate, or Severe using the following intensity grades definitions:

- **Mild** – Awareness of signs or symptom, but easily tolerated
- **Moderate** – Discomfort, enough to cause interference with usual activity
- **Severe** – Incapacitating with inability to perform usual activity.

Note the distinction between an AE with an intensity of “severe” and a “serious” AE, a severe event is not necessarily a serious event. For example, a headache may be severe but would not be classified as serious unless it met one of the SAE criteria.

